15.3 Appendix 3 HADS

Hospital Anxiety and Depression Scale (HADS)
(please check box for single best answer for each question)

1. I feel tense or wound up	 most of the time	 a lot of the time	 occasionally	 not at all
2. I still enjoy the things I used to enjoy	 definitely as much	 not quite as much	 only a little	 hardly at all
3. I get a sort of frightened feeling as if something awful is about to happen	 quite badly	 not too badly	 a little	 not at all
4. I can laugh and as see the funny side of things	 as much as I always could	 not quite so much now	 definitely not so much now	 not at all
5. Worrying thoughts go through my mind	 a great deal of the time	 a lot of the time	 from time to time	 only occasionally
6. I feel cheerful	 not at all	 not often	 sometimes	 a lot
7. I can sit at ease and feel relaxed	 definitely	 usually	 not often	 not at all
8. I feel as if I am slowed down	 nearly all the time	 very often	 sometimes	 not at all
9. I get a sort of frightened feeling like butterflies in the stomach	 not at all	 occasionally	 quite often	 very often
10. I have lost interest in my appearance	 definitely	 I don't take so much care as I should	 I may not take quite as much care	 I take just as much care as ever
11. I feel restless as if I have to be on the move	 very much	 quite a lot	 not very much	 not at all
12. I look forward with enjoyment to things	 as much as ever	 rather less than I used to	 definitely less than before	 hardly at all
13. I get sudden feelings of panic	 very often	 quite often	 not often	 not at all
14. I can enjoy a good book or program	 often	 sometimes	 not often	 very seldom

15.4 Appendix 4 Patient Activation Measure

PATIENT ACTIVATION MEASURE

Below are some statements that people sometimes make when they talk about their health. Please indicate how much you agree or disagree with each statement as it applies to you personally by circling your answer. If the statement does not apply to you, circle N/A.

Your answers should be what are true for you and not just what you think the doctor wants you to say.

When all is said and done, I am the person who is responsible for managing my health condition	Disagree Strongly	Disagree	Agree	Agree Strongly	N/A
Taking an active role in my own health care is the most important factor in determining my health and ability to function	Disagree Strongly	Disagree	Agree	Agree Strongly	N/A
I am confident that I can take actions that will help prevent or minimize some symptoms or problems associated with my health condition	Disagree Strongly	Disagree	Agree	Agree Strongly	N/A
I know what each of my prescribed medications do	Disagree Strongly	Disagree	Agree	Agree Strongly	N/A
I am confident that I can tell when I need to go get medical care and when I can handle a health problem myself	Disagree Strongly	Disagree	Agree	Agree Strongly	N/A
I am confident I can tell my health care provider concerns I have even when he or she does not ask	Disagree Strongly	Disagree	Agree	Agree Strongly	N/A
I am confident that I can follow through on medical treatments I need to do at home	Disagree Strongly	Disagree	Agree	Agree Strongly	N/A
I understand the nature and causes of my health conditions(s)	Disagree Strongly	Disagree	Agree	Agree Strongly	N/A
I know the different medical treatment options available for my health condition	Disagree Strongly	Disagree	Agree	Agree Strongly	N/A
I have been able to maintain the lifestyle changes for my health that I have made	Disagree Strongly	Disagree	Agree	Agree Strongly	N/A
I know how to prevent further problems with my health condition	Disagree Strongly	Disagree	Agree	Agree Strongly	N/A
I am confident I can figure out solutions when new situations or problems arise with my health condition	Disagree Strongly	Disagree	Agree	Agree Strongly	N/A
I am confident that I can maintain lifestyle changes like diet and exercise even during times of stress	Disagree Strongly	Disagree	Agree	Agree Strongly	N/A

15.5 Appendix 5 Self Efficacy Survey

SELF-EFFICACY TO PERFORM SELF-MANAGEMENT BEHAVIORS

We would like to know **how confident** you are in doing certain activities. For each of the following questions, please write the number that corresponds to your confidence that you can do the tasks regularly at the present time.

1) SE Exercise Regularly

Not at all confident 1 2 3 4 5 6 7 8 9 10 Totally confident

How confident are you that you can...

- a. Do gentle exercises for muscle strength and flexibility three to four times per week (range of motion, using weights, etc.)? _____
- b. Do an aerobic exercise such as walking, swimming, or bicycling three to four times each week? _____
- c. Exercise without interfering with your ostomy equipment? _____

2) SE Get Ostomy Information

Not at all confident 1 2 3 4 5 6 7 8 9 10 Totally confident

How confident are you that you can...

- a. Get ostomy information from your health care system? _____
- b. Get ostomy information from community resources? _____
- c. Get ostomy information from resources on the web? _____
- d. Get ostomy information from a peer who has an ostomy? _____

3) SE Obtain Help From Community, Family, and Friends

Not at all confident 1 2 3 4 5 6 7 8 9 10 Totally confident

How confident are you that you can...

- a. Get family and friends to help you with the things you need help with (such as household chores, transportation) ? _____
- b. Get help with the things you need help with (such as household chores, transportation) from resources other than friends or family, if needed? _____
- c. Get family and friends to help you with ostomy care? _____
- d. Get emotional support from friends and family (such as listening or talking over your problems) ? _____
- e. Get emotional support from resources other than friends or family, if needed? _____

4) SE Communicate with Physician

Not at all confident 1 2 3 4 5 6 7 8 9 10 Totally confident

How confident are you that you can...

- a. Ask your health care providers things about your ostomy concerns? _____

- b. Discuss openly with your health care providers any personal problems that may be related to your ostomy or surgery? _____
- c. Work out differences with your health care providers when they arise? _____

5) SE to Manage Disease in General

Not at all confident 1 2 3 4 5 6 7 8 9 10 Totally confident

How confident are you that you can...

- a. Having an illness often means doing different tasks and activities to manage your ostomy. How confident are you that you can do all the things necessary to manage your ostomy on a regular basis? _____
- b. Judge when the changes in your condition mean you should visit a health care provider? _____
- c. Do the different tasks and activities needed to manage your ostomy so as to reduce your need to see a health care provider? _____
- d. Reduce the emotional distress caused by your ostomy so that it does not affect your everyday life?
- e. Manage your ostomy care? _____?

6) SE Social/Recreational Activities

Not at all confident 1 2 3 4 5 6 7 8 9 10 Totally confident

How confident are you that you can...

- a. Continue to do your hobbies and recreation? _____
- b. Continue to do the things you like to do with friends and family (such as social visits and recreation)? _____
- c. Travel distances from your home (if you desire)? _____

7) SE Manage Ostomy Symptoms

Not at all confident 1 2 3 4 5 6 7 8 9 10 Totally confident

How confident are you that you can...

- a. Reduce your physical discomfort or pain? _____
- b. Keep the leakage from interfering with the things you want to do? _____
- c. Keep the gas from interfering with the things you want to do? _____
- d. Keep any odor you have from interfering with the things you want to do? _____
- e. Maintain the integrity of your skin (prevent skin breakdown) ? _____
- f. Control any other ostomy-related problems you have so that they don't interfere with the things you want to do? _____

8) SE Control/Manage Depression

Not at all confident 1 2 3 4 5 6 7 8 9 10 Totally confident

How confident are you that you can...

- a. Keep from getting discouraged when nothing you do seems to make any difference? _____

- b. Keep from feeling sad or down in the dumps? _____
- c. Keep yourself from feeling lonely? _____
- d. Do something to make yourself feel better when you are feeling lonely? _____
- e. Do something to make yourself feel better when you are feeling discouraged? _____
- f. Do something to make yourself feel better when you feel sad or down in the dumps? _____

15.6 Appendix 6 Ostomy Knowledge Survey**OSTOMATE KNOWLEDGE SURVEY**

1. It is important that one knows the specific type of ostomy he/she has because:
 - A. Each has its own unique management style.
 - B. There are different types of equipment that might be better.
 - C. It helps communication with an Ostomy Nurse.
 - D. All of the above.

2. When using a solid skin barrier or wafer, it should be cut to fit at the base of the stoma allowing:
 - A. Snug with the stoma
 - B. 1/8 inch clearance from the stoma.
 - C. 1/2 inch clearance from the stoma.
 - D. It does not matter the distance from the stoma.

3. If the wafer is not properly fitted
 - A. The stoma could be traumatized.
 - B. Leakage may be more likely.
 - C. The peristomal skin could breakdown.
 - D. All of the above.

4. When cleansing the peristomal area, the proper method would be accomplished by using
 - A. Wet warm washcloth
 - B. Alcohol wipes
 - C. Baby wet wipes
 - D. Dial soap

5. An ostomy pouching system should typically be changed
 - A. Whenever you have time to change.
 - B. Every 4-7 days.
 - C. Whenever there is stool in the pouch.
 - D. Once a week.

6. An ostomy pouch should be emptied when the pouch is
 - A. Full
 - B. Half full
 - C. One third full
 - D. Every day

7. Which of the following must the ostomate AVOID?
 - A. All sports activities
 - B. Sexual intimacy
 - C. Small children
 - D. All of the above.
 - E. None of the above.

8. Which of the following is accurate regarding the urine of a urostomate? (Answer only if you have a urostomy (urinary diversion))
- A. It may contain some mucous shreds.
 - B. If persistent bleeding is evident, the urostomate should notify urologist or go to ER.
 - C. If no urine is produced in 4 hours, the urostomate should consult urologist or go to ER.
 - D. Urine should be transparent.
 - E. All of the above.
9. The purpose of colostomy irrigation is (Answer only if you have a colostomy):
- A. To regulate and control bowel function.
 - B. To keep the bowel clean.
 - C. To eliminates gas.
 - D. Decrease time spent caring for my ostomy.
10. Some foods that may cause problems for the ileostomate include:
- A. Corn/popcorn
 - B. Nuts
 - C. Seeds
 - D. All of the above.
11. Regarding pouching systems:
- A. One should never change pouching systems.
 - B. One should always change a pouching system if there are frequent leaks.
 - C. It is reasonable to look at new products at regular intervals.
 - D. Pouching systems have similar costs.
 - E. None of the above.

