 - ii. >20% questions missing (or more than 1 response to choose best answer questions), not counting open-ended questions, appropriately skipped questions, or sensitive area questions listed below
 - iii. The following sensitive questions will not be counted in determining need for callback, nor asked during a call back if missing:
 1. COH-QOL-CRC intimacy item “Has your ostomy interfered with your ability to be intimate?”
 2. COH-QOL-CRC spiritual item “Is support you receive from personal spiritual activities such as prayer or meditation sufficient to meet your needs?”
 3. COH-QOL-CRC religious item “Is support you receive from religious activities such as going to church or synagogue sufficient to meet your needs?”
 4. COH-QOL-CRC Sexual activity items.
 5. COH-QOL-CRC race/ethnicity items
 6. COH-QOL-CRC household income item
 7. Open ended questions will not be counted towards a call back or asked in a callback.
- d. If the participant declines to answer a question again during the call back, initials will be placed by the question and the question will be left blank.

8.2.10 Shipping paper surveys to Data Core. Hard copy surveys will be reviewed for PHI, which will be masked if present, and scanned to a PDF file within a secure server at each site. These PDF files will be uploaded into RedCap, using a built-in application called Send-It, in which files stay behind the RedCap firewall until retrieved by intended RedCap user recipient from the same RedCap project. Files can only be downloaded by the designated recipient, and that recipient must have log-in capability to RedCap and assignment to the specific project. Within RedCap on the “My Projects” page (one level up from the PCORI project), there is a tab on the right called “Send-it” with an envelope icon. Instructions within the tab are clear to follow. Each PDF file should have only one subject and one event (baseline, interim, followup). Files should be named according to a consistent naming convention for each site based on subject ID number and event (e.g., 1001 baseline.pdf; 2003 followup.pdf, etc.). Data Core staff will download PDF files from Send-it to a secure University of Arizona server and key data responses into the RedCap database. PDF files will be deleted at end of the study.

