8.3 Curriculum (Appendix 1)

This will also be sent electronically.

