9.0 STUDY PLAN

9.1 Usual Care

The UC control program is designed to compare OSMT to usual care to capture the Hawthorne effect. The final intervention for the UC group includes:

- 1) Recommending the patient has met at least once with an ostomy nurse (while likely to have happened in the peri-operative period, it may not be universal);
- 2) Providing the booklet published by The Wound, Ostomy, and Continence Nurses' Society entitled "Basic Ostomy Skin Care: A Guide for Patients and Health Care Providers," with instructions on how to use it;
- 3) Local support group contact information;
- 4) Encouraging patients to have seen their surgeons at least once in follow-up after surgery;
- 5) Contact information for local nutritional and physical therapists; and
- 6) Ostomy nurse contact information. If patients have specific questions about materials, the research coordinator will clarify the content and encourage the patient to call their physician or ostomy nurse about a continuing problem. These resources will also be given to those in the OSMT program.

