11.0 CRITERIA FOR EVALUATION AND ENDPOINT DEFINITIONS

Study instruments and endpoints	Endpoints
Patient Activation Measure (PAM). The PAM uses a uni-dimensional, probabilistic Guttman-like scale that reflects a developmental model of activation that involves four stages: (1) believing the patient role is important, (2) having the confidence and knowledge necessary to take action, (3) actually taking action to maintain and improve one’s health, and (4) staying the course even under stress. High internal consistency (alpha .87) and construct validity have been reported.	PAM (continuous 0 to 100, where 100 is most activated) Level 1: May not yet believe that the patient role is important (PAM ≤ 47.0) Level 2: Lacks confidence and knowledge to take action (PAM 47.1 to 55.1) Level 3: Beginning to take action (PAM 55.2 to 67.0) Level 4: Has difficulty maintaining behaviors over time (PAM ≥ 67.1)
Self-Efficacy to Perform Ostomy Self-Management Behaviors. Modified from Lorig	SE Ostomy Self-Management (1 to 10, where 10 is most confident)

Study instruments and endpoints	Endpoints

and colleagues' Self-Efficacy to Perform Self-management Behaviors Scale, an outcome measure for Chronic Disease Management Interventions, this scale represents 8 domains with reported Cronbach's alpha for original scales: physical activity (.83), information seeking (NA), support (.77), communication with HC providers (.90), ostomy management (.87), social and recreational (.82), symptom management (.91), and depression (.92).
	

COH-QOL-CRC Scale. The City of Hope QOL-Ostomy questionnaire (developed by Consultant [name]) was designed for all adult ostomates, and has a 4-dimensional HRQOL (physical, psychological, social and spiritual well-being) framework gathering demographic, clinical history, personal (e.g., diet, work, and activity) and clinical data. Reported Cronbach's alphas are .94 total scale and .80-.90 subscales. Family version will be used for caregivers.
	
COH-QOL-CRC Total COH-QOL-CRC Physical COH-QOL-CRC Psychological COH-QOL-CRC Social COH-QOL-CRC Spiritua1 (0 to 10 scores)

Ostomy Knowledge Questionnaire. This brief survey, derived at City of Hope, was modified for the pilot study and further adapted by the study team to ensure major topics were included.
	
Knowledge score (0 to 11)

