12.0 STATISTICAL CONSIDERATIONS

12.1 General. Aim 1 will be analyzed with linear mixed models for repeated measures. Aim 2 will utilize a variety of sources and methods to enumerate the intervention program and ostomy-related family resources in each study arm.

If a subject misses Session 3 or Session 4 or both, they can make up the missed session(s) with the next 1 or 2 scheduled groups. If they miss both chances to make up the sessions, they

will be asked to do the surveys and will be analyzed as a separate group using an intent-to-treat contrast.

12.2 Aim 1: Using our enhanced telehealth techniques, determine if **patient activation**, self-efficacy, ostomy-related knowledge, and HRQOL will be improved and sustained over time in the online interactive communication Ostomy Self-Management Telehealth program (OSMT) curriculum compared to a UC group.

Under an intent-to-treat approach, change in outcomes will be evaluated longitudinally with linear mixed models, testing the effect of study arm adjusted for potential confounders. Such models evaluate both associations and rates of change, accounting for within-subject correlation. The Primary Outcome will be PAM. Secondary Outcomes include SE, COH-QOL-CRC scales, and Ostomy Knowledge. Post hoc contrasts will evaluate effect of training (baseline to post) and whether effect is sustained after training (6 month post to follow-up). Standard multivariable modeling procedures will be used to select or eliminate potential confounding variables, starting with candidate variables that are biologically plausible or found to be associated with endpoint change scores (baseline vs. follow-up) in bivariate analyses with a p-value of less than 0.20. Potential candidate covariates and confounders include (but are not limited to) CG participation in training sessions, depression (HADS), time since surgery, ostomy type, age, sex, stage, anticipated permanence of ostomy, and pre- or post-surgical radiation or chemotherapy. We will explore potential interaction for plausible effect modifiers, such as gender, or having a CG.

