3. Skin Adhesive Removers
 - a. Used to remove adhesive after applying the wafer and pouch (Not recommended for routine use)
 - b. Some ostomates find it easier to reapply wafer if some adhesive is left on the skin
4. Deodorizers
 - a. Used to reduce odor
 - b. Tablet form you eat or drop into pouch
 - c. Vents are also available to apply to pouch to release gas and deodorize it as it passes through the vent
5. Stoma Patches and Caps
 - a. Used to prevent leakage when colostomy is irrigated and stool is controlled
 - i. Pouch Covers: A cover that goes around your pouch to absorb sweat and to cover the contents of the pouch

- ii. Convexity
 - a) Skin irritation can occur from leakage on the skin
 - b) Use of convex wafer makes the stoma protrude from skin and redirects flow of urine or feces into pouch
- 6. Pouches
 - a. One Piece System
 - i. The wafer and pouch are attached as one unit
 - ii. Advantages
 - a) Quick and easy to use
 - b) Less Bulky (One vs. Two Parts)
 - b. Two-Piece System
 - i. The wafer and pouch are two separate pieces and are attached by attaching the wafer connector to the pouch connector
 - ii. Advantages
 - a) Can change bag size for different moments
 - b) Easier to relieve gas
 - iii) Disadvantage
 - a) Since attached wafer to bag, error may occur causing leakage
 - b) May be difficult to attach wafer to pouch and abdomen if ostomate is visually impaired
- 7. Belts
 - a. Some ostomates prefer to wear a belt
 - i. Attach to wafers using a special tag
- 8. Daily Care
 - a. Colostomy bag should be emptied when reaches 1/3 gas or stool
 - i. Achieve pouch adherence up to 5 days
 - b. If you use the reusable pouches, make sure they are thoroughly cleaned with mild soap and water
- 9. Disposal of ostomy bag
- 10. Reviewing Routines
- 11. Emergency Kits

Session 1 Assignments (5 min)

C. Assignments

1. Goal Development for Session 2

When you completed the first survey packet, it contained a goal development sheet. We are now going to ask you to please describe the goals you have in regards to your ostomy care.

2. Monitoring timed daily outputs/Nutrition Log by Time

Please monitor your daily bowel movements and how they are affected by different situations or foods. These will be discussed at upcoming sessions and will be useful if issues were written down.

Session 1 Resources (5 min)**D. Resources**

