1. Ostomy can create sexuality/Intimacy problems for ostomates and caregivers

An ostomate is influenced in many ways by their ostomy. Your partner may not want to be intimate because of the ostomy. It is important for you to encourage dialogue with your spouse/Significant other/Friend concerning intimacy and the other issues discussed in this training session.
2. Preoperative information from surgeon and if enough time to adjust to the idea of sexual impairment
 - a. What did you understand about the process from surgeon?
 - b. Did radiation therapy cause sexual problems before the ostomy?

Caregiver Session Resources (10 min.)

E. Resources

Do you have the resource list given to the ostomate? If not, would you like one either emailed or paper mailed to you? *If you wish to contact one of the Peer Ostomates outside of this session, their phone numbers are: [read off name and phone number of Peers]*

Connectivity

F. Prior to disconnection, we want to ask on a scale of 1-4 your ability to connect to the session and your impression of the technology.

Session 3 - Introduction (5 min., Session 3, Ostomate folder)

We want to remind everyone that participation is completely voluntary and you may withdraw at any time. The sessions are confidential only first names will be used. Please respect the privacy of others. This session focuses on nutrition, healthy lifestyles, and finances.

We will now do a quick roll call using first names only. Please also tell us what kind of device you are using (e.g. iPad, Apple PC, iPhone, etc.).

Are there any questions from the last session?

Session 3 Nutrition and Education Timing (15 min)A. Nutrition and education timing, specific foods (**Group Discussion**)

1. Review of nutritional logs as a group
 - a. What foods give you gas?
 - b. What foods increase the number of daily bowel movements?
 - c. What foods are helpful

Session 3 Healthy Lifestyles (10 min)

B. Implementing a healthy living style

There are many ways of implementing healthy lifestyles. Below are a few items related to healthy lifestyles:

1. Daily activities

The goal is to do everything you did before your surgery. What daily activities did you do before your surgery? Some examples are:

- a. Lawn Mowing
- b. Motorcycle Riding
- c. Leisure Swimming

Are you able to still do these activities?

2. Exercise

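### The ostomy knowledge test does not ask for answers from memory, and the curriculum, apparently sent to OSMT participants only, gives or points to four of its answers, so look-up could add to the OSMT score

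*Protocol*

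**What the plan says.** **Role of the test.** Protocol 12.2 and the SAP both state: "Secondary Outcomes include SE, COH-QOL-CRC scales, and Ostomy Knowledge". Hypotheses 1.2.1 and 1.2.2 concern greater and sustained improvement in knowledge with OSMT. Section 11.0 scores the test from 0 to 11.

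**How it is taken.** Sections 8.0 and 8.2 provide for mailed paper forms or, preferably, a RedCap web link at baseline, after the sessions and at 6 months. The Session 4 script asks OSMT participants to complete the surveys soon after that session. No supervision is described. Appendix 6 goes straight to question 1, with no line on how to answer.

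**Who holds what.** Section 8.3, which sits under 8.0 Mailed Packets, lists the curriculum and says only: "This will also be sent electronically". Section 9.1 lists what usual care receives: a skin-care booklet, support-group, therapist and ostomy-nurse contacts, and advice to see a nurse and surgeon. The curriculum is not on that list. Section 9.1 adds: "These resources will also be given to those in the OSMT program".

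**Overlap of test and curriculum.** Item 6 of Appendix 6 reads "An ostomy pouch should be emptied when the pouch is" and offers full, half full, one third full or every day. The Session 1 skills lab in Appendix 1 says "Colostomy bag should be emptied when reaches 1/3 gas or stool".

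**The concern.** A factual test completed alone can be answered from whatever is on the desk. If one arm holds a document that covers part of the test and the other does not, the between-arm difference mixes what people learned with what they could find. Randomization does not remove this, because the asymmetry arises after assignment. Section 12.11 describes randomized trials as not usually prone to information bias. Neither document has a safeguard or sensitivity analysis for look-up.

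At stake is how the knowledge parts of hypotheses 1.2.1 and 1.2.2 are read. The 6-month comparison is exposed too, because nothing asks participants to return their materials.

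**Working it through.** **Step 1: match the items to the curriculum.** The documents print no answer key, so an answer here means the option to which the curriculum text leads.

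| Item | Curriculum text (Appendix 1) | Match |
|---|---|---|
| 6, when to empty | Session 1 skills lab: one third | Stated directly |
| 5, how often to change | Session 1 skills lab: adherence for up to 5 days | Points to the 4-7 day option |
| 9, purpose of irrigation (colostomy only) | Session 1, patches and caps: irrigated colostomy, stool controlled | Points to the regulate-and-control option |
| 10, problem foods | Session 1: nuts and seeds among the examples | Points to the all-of-the-above option |
| 3, 7, 11 | Leakage and skin irritation; "The goal is to do everything you did before your surgery"; try another pouching system | Hints only |
| 1, 2, 4, 8 | Nothing that settles them | None |

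So 1 of 11 items is stated and 3 more are effectively answered. Item 9 applies to colostomies only, so the number of exposed items, k, is 4 for colostomates and 3 for others.

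**Step 2: reproduce the plan's precision.** Section 12.13 has no row for Knowledge. Its table for the other scales follows from

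detectable difference = SD × (t₀.₉₇₅ + t₀.₈₀) × √[(2/n) × (1 − ρ²)/2],

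with ρ = 0.60 and two-sided alpha 0.05. For PAM (SD 13) this gives 3.39, 3.51 and 3.64 at n = 75, 70 and 65 per arm, against 3.4, 3.5 and 3.6 in the table. At n = 75 the standard error is √(2/75 × 0.32) = 0.092 SD and the detectable difference is about 0.26 SD (3.4/13).

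**Step 3: put this on the knowledge scale.** Assumption: SD 1.5 to 2.0 points. The detectable difference is then 0.26 × 1.5 = 0.39 to 0.26 × 2.0 = 0.52 points.

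**Step 4: size of a look-up shift.** Let p₀ be the chance of a correct answer without look-up and f the share of OSMT participants who look up, with none in usual care. Then

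shift = k × (1 − p₀) × f.

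Neither p₀ nor f is in the documents. Over k = 3 to 4, p₀ = 0.5 to 0.9 and f = 10% to 50%, the shift runs from 3 × 0.1 × 0.1 = 0.03 to 4 × 0.5 × 0.5 = 1.0 points.

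**Step 5: how often such a shift alone would reach p < 0.05** (75 per arm, no other arm difference; the range is SD 2.0 to SD 1.5):

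| Assumptions | Shift | Table's precision (variance factor 0.32) | Compound symmetry (factor 0.44) |
|---|---|---|---|
| k = 4, p₀ = 0.9, f = 25% | 0.10 | 8-11% | 7-9% |
| k = 4, p₀ = 0.7, f = 25% | 0.30 | 37-58% | 28-45% |
| k = 4, p₀ = 0.7, f = 50% | 0.60 | 90-99% | 79-96% |

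The factor 0.44 is (1 + ρ)/2 − ρ². It applies if the two follow-up scores remain correlated after adjustment for baseline.

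**The case against.** Several points on the other side have force.

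- **Possession is inferred.** Section 8.3 names no recipient, and parts of Appendix 1 read as a facilitator's script. Its place under Mailed Packets, its references to the participant's packet and folder, and its absence from 9.1 make OSMT-only receipt likely but not certain.
- **Usual care has sources too.** Both arms get the booklet and nurse contacts, and either arm can search the web. The booklet's contents are not in the documents, so the net asymmetry is unknown. Any look-up in usual care shrinks the shift in step 4.
- **Only item 6 is close to verbatim.** Items 5, 9 and 10 need a short inference.
- **Baseline look-up works the other way.** If the curriculum arrived before the baseline test, look-up there would raise the OSMT starting score and reduce its gain. The documents do not say which comes first.
- **An instruction may exist elsewhere.** Section 8.0 mentions a cover letter that is not shown.

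These points limit the size and certainty of the problem. They do not supply the missing instruction.

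A reader might go further and infer that the knowledge difference measures look-up instead of knowledge. The documents do not support that: the sessions teach the same points, so look-up would come on top of real learning.

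A reader might also infer that the call-back rule in 8.2.9 turns honest blanks into guesses. That rule is aimed at questions that appear to have been skipped inadvertently, and 8.2.9(d) leaves an item blank if the participant declines again. It applies to both arms.

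**Conclusion.** The point stands as a measurement weakness in one secondary outcome. The test is unsupervised, has no answer-unaided line, and overlaps on up to four items with a document that OSMT participants very probably hold and usual-care participants probably do not. Look-up and learning raise the same score, and the data as collected could not tell them apart.

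The size cannot be derived from the documents. Under the stated assumptions it runs from negligible (0.03 points) to enough to produce a significant difference unaided (0.6 points or more). Every figure rests on an assumed SD, look-up share and baseline success rate, and on no look-up in usual care. The finding does not show that bias will occur, and PAM is not touched. It is worth acting on because the remedy is nearly free.

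**What to change.** 1. Add one line at the head of Appendix 6, on paper and in RedCap, for both arms and all remaining rounds: *Please answer from memory, without using course materials, the booklet, the internet or another person.*
2. Add to the SAP a sensitivity analysis of the knowledge score without items 5, 6, 9 and 10. This leaves 6 applicable items for colostomates (10 − 4), 6 for ileostomates (9 − 3) and 7 for urostomates (10 − 3). State that it is conservative, because the sessions also teach the omitted points.

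The cost is a sentence on the form, a RedCap text edit and one further model. The line cannot be enforced, and rounds already collected were taken without it, so the report should say which rounds carried it.

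Two further changes are not recommended: exempting this form from call-backs, and telling participants to leave unknown items blank and scoring blanks as wrong. The second would make the score depend on willingness to guess. OSMT aims to raise confidence, so that could introduce a new difference between arms.
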